Title: Prospective, multicenter, single-arm phase II clinical trial for biomarker validation in patients with advanced and / or metastatic colorectal cancer with KRAS gene not mutated treated with chemotherapy plus biweekly cetuximab as first-line therapy.

Study Phase: Phase II

Indication:

Advanced and / or metastatic colorectal cancer (CCRA)

Principal Objective:

Validation of the biomarkers BRAF, IGF1P / MMP7 (DP) and PI3K-PTEN to predict PFS in patients with advanced and / or metastatic colorectal cancer with non-mutated KRAS treated with standard chemotherapy plus biweekly cetuximab as first-line therapy.

Secondary Objectives:

Secondary biological markers (MMP-7, IGF-1 and IGFBP3) will be analyzed in serum and tumor tissue to predict acquired resistance.

OS based on proposed classification

Objective response according to RECIST 1.1 (*E.J. Cancer 2009; 228-47*)

Safety of administration of cetuximab 500 mg / m² every 2 weeks.

Clinical Hypothesis:

Our hypothesis is that the proposed markers will make it possible to select those patients who will benefit the most from biweekly cetuximab treatment.

Study design:

Single-arm prospective phase II clinical trial.

Prior to inclusion in the trial and to confirm eligibility, the investigator or designee will review the status of KRAS, BRAF, IGF1P / MMP7 (DP) and PI3K-PTEN, existing radiological images in addition to any other relevant clinical documents (reports, notes, etc.) to confirm that the subject has previously untreated advanced and / or metastatic colorectal cancer.

FOLFIRI (m) / FOLFOX6 (m) will be administered once every 2 weeks until 6 months of treatment, disease progression (PE), or unacceptable toxicity. Cetuximab will be administered every 2 weeks until disease progression. If patients do not show progression after 6 months of treatment with FOLFIRI (m) and FOLFOX6 (m), they will continue to receive biweekly cetuximab as monotherapy until progression.

Subjects who stop receiving FOLFOX6 (m) / FOLFIRI (m), for example due to toxicity, may receive biweekly cetuximab as monotherapy until disease progression. Following discontinuation of biweekly cetuximab, the treatment period will end and subjects will attend a follow-up safety visit

Single-arm, multicenter, prospective phase II clinical trial for biomarker validation in patients with advanced and / or metastatic colorectal cancer with non-mutated KRAS gene treated with chemotherapy plus biweekly cetuximab as first-line therapy

30 ± 3 days later.

Throughout the trial, subjects will undergo tumor response assessment (using the revised [RECIST 1.1] Solid Tumor Response Assessment Criteria) every 12 weeks (three months) until disease progression. In subjects with symptoms that indicate disease progression, tumor response should be assessed at the time of symptoms.

Biologic study

K-RAS, in patients who do not have a determination, and other markers of tumor tissue will be measured at the Navarra University Clinic (CUN) and the markers of the blood samples will be measured at the Hospital Clínic de Barcelona (HCB).

Biomarkers will be measured prior to patient enrollment. In addition, blood samples will be collected every 3 months until disease progression.

Endpoints:

Principal endpoint:

The main endpoint is progression-free survival comparing two cohorts, which will be defined according to the classification based on the predictive capacity of the response of the biomarkers.

Secondary endpoint:

Secondary biological markers in serum and tumor tissue will be analyzed to predict acquired resistance.

OS based on proposed classification

Objective response according to RECIST 1.1 (*E.J. Cancer 2009; 228-47*) (objective response rate)

Response duration

Safety (Type, frequency and intensity of appearance of Adverse Events)

Single-arm, multicenter, prospective phase II clinical trial for biomarker validation in patients with advanced and / or metastatic colorectal cancer with non-mutated KRAS gene treated with chemotherapy plus biweekly cetuximab as first-line therapy

Sample size:

A sample size of 170 patients will be needed.

Principal Inclusion Criteria:

Patients, men or women aged 18 years or older, with advanced and / or metastatic colorectal cancer with non-mutated KRAS, histologically or cytologically confirmed and radiologically evaluable, ECOG performance status of 0 to 2 with adequate hematological, renal and hepatic function and informed consent signed.

Ver listado completo de Criterios de Inclusión en el apartado 6.1 del protocolo

Principal Exclusion Criteria:

Patients who have received prior systemic treatment for metastatic colorectal carcinoma will be excluded from the trial. Patients with previous surgery for metastases (liver, lung or other), metastases in the central nervous system or with significant cardiovascular disease will also be excluded.

Ver listado completo de Criterios de Exclusión en el apartado 6.2 del protocolo

Dosage and administration of the investigational product:

FOLFOX6 (m) chemotherapy regimen:

FOLFOX6 (m) chemotherapy will be given on day 1 of each 14-day treatment cycle. FOLFOX6 (m) will be administered at the following doses:

85 mg / m² of oxaliplatin infusion i.v. 120 minutes on day 1 of each cycle.

400 mg / m² leucovorin infusion i.v. 120 minutes on day 1.

One i.v. bolus (2 to 4 minutes) of 400 mg / m² 5-FU on day 1.

5-FU in continuous infusion 2400 mg / m² administered by ambulatory pump over a period of 46-48 hours

FOLFIRI (m):

FOLFIRI (m) chemotherapy will be administered on day 1 of each 14-day treatment cycle. FOLFIRI (m) will be administered at the following doses:

Irinotecan 180 mg / m² in infusion i.v. 120 minutes on day 1 of each cycle.

Leucovorin 200 mg / m², in infusion i.v. 120 minutes on day 1.

One i.v. bolus (2 to 4 minutes) of 400 mg / m² 5-FU on day 1.

5-FU in continuous infusion 2400 mg / m² administered by ambulatory pump over a period of 46-48 hours.

CETUXIMAB:

Administer 500 mg / m² i.v. every 2 weeks.

Single-arm, multicenter, prospective phase II clinical trial for biomarker validation in patients with advanced and / or metastatic colorectal cancer with non-mutated KRAS gene treated with chemotherapy plus biweekly cetuximab as first-line therapy

It is recommended to administer cetuximab first and start with the administration of FOLFOX6 (m) / FOLFIRI (m), at least one hour after cetuximab administration has ended.

Statistical considerations:

Prospective, multicenter, phase II clinical trial designed for the validation of predictive tumor biomarkers in patients with metastatic colorectal cancer and tumor with non-mutated KRAS, treated with chemotherapy and biweekly cetuximab as first-line treatment.

The main objective of this trial is to validate the biomarkers BRAF, IGF1P / MMp7 (DP) and PI3K-PTEN to predict PFS in patients with advanced and / or metastatic colorectal cancer with non-mutated KRAS treated with standard chemotherapy plus biweekly cetuximab as therapy. From first line.

Two groups will be defined based on the classification constructed from the clinical variables and the proposed biomarkers.

A minimum difference of 20% (60 vs. 40%) in PFS is expected at 12 months between groups and with the following assumptions:

Alpha error (bilateral): 5%

Beta error: 20%

The number of patients required is 155 patients. Assuming 10% non-evaluable patients, a total of 170 patients will be included.

The Cox regression analysis will be performed with the experimental biomarkers and the following prognostic variables (LDH, functional status, age, limited resectable disease (<3 nodules and <5cm). A classification will be performed using the most discriminatory variables. The classification It will be carried out with all the clinical variables of impact in the univariate analysis including the 4 clinical variables (LDH, functional status, age, limited resectable disease <3 nodules and <5 cm) and the 3 pathways previously described (BRAF, DP and PTEN- PI3K) .The classification will be carried out with the variables with the greatest impact in the multivariate analysis.

The proposed sample size ensures the construction of a consistent multivariate analysis.

[figure not shown]
The analysis of the main variable “progression-free survival comparing two cohorts, which will be defined according to the classification based on the prediction capacity of the response of the biomarkers” and the secondary variable “efficacy”, will be based on the revised version of RECIST 1.1 criteria (Appendix E) for the intention-to-treat analysis group.

Changes in laboratory values and vital signs will be summarized with descriptive statistics.

Single-arm, multicenter, prospective phase II clinical trial for biomarker validation in patients with advanced and / or metastatic colorectal cancer with non-mutated KRAS gene treated with chemotherapy plus biweekly cetuximab as first-line therapy

Sponsor:

Grupo Español Multidisciplinar en Cáncer Digestivo (GEMCAD)

Name of the Organization responsible for Monitoring:

Secretaría Técnica GEMCAD

Schedule and expected completion date:

[figure not shown]
Start date: Second quarter 2010

First Inclusion Date: Fourth quarter 2010

Recruitment period: 24 months

End of Trial Period: Year 2014

Study scheme

a Day 1 = day of the first treatment administration.

b Subjects' tumor response will be assessed every 12 weeks, throughout the trial until PE (per revised RECIST 1.1 criteria) or withdrawal from the study.

c Subsequent cycles could be delayed due to toxicities associated with cetuximab or chemotherapy.

d All subjects who permanently discontinue treatment (discontinuation is considered completion of all treatment) for any reason will undergo a follow-up safety assessment 30 days \pm 3 days after the last dose of treatment. After the safety follow-up visit, subjects who have not progressed will be followed up every 12 weeks as defined in the study. Subjects who undergo surgery for metastases should follow the controls every 12 weeks as established in the protocol. In case of progression by RECIST 1.1 criteria ., Subjects will be monitored for disease status, subsequent cancer treatment, and survival (long-term follow-up).

e All subjects who discontinue treatment prior to disease progression (eg, due to unacceptable toxicities) will be followed up for PFS (eg, radiographic tumor assessments) every 12 weeks until the progression of the disease or the end of the study (unless the reason for abandoning the study was the total withdrawal of consent).

F. The end of treatment is understood to be the last day the patient has received the last drug of the combination under test (FOLFOX6 (m) / FOLFIRI (m) / Cetuximab). The safety visit should be carried out 30 \pm 3 days after the end of the treatment, regardless of the cause that caused it. If the patient has not progressed, imaging and biomarker determinations should continue every 12 weeks until progression as specified in this protocol.

g. In order to mobilize any biological sample, the signing of the informed consent will be mandatory. If the patient already has a previous determination of the status of the KRAS gene, he can be included in the test without it being necessary to re-determine the mutational status of K-RAS.

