These data were presented together with their update according to the mutational status of KRAS and BRAF (determined in 83% of patients), in the past ASCO GI (Van Cutsem E, Lang I, Folprecht G, et al. Cetuximab plus Folfiri in the treatment of metastatic colorectal cancer (mCRC): the influence of KRAS and BRAF biomarkers on outcome: updated data from the Crystal trial. Presented at: ASCO gastrointestinal Cancers Symposium. January 2010 (Abstract 281), maintaining superiority in terms efficacy of the combination of QT with cetuximab in native KRAS patients. These results were superior in patients with native KRAS and native BRAF, and the presence of mutated BRAF worsened the results, regardless of the treatment used, the authors concluding that the BRAF mutation is a negative prognostic factor in mCRC.

OPUS 20 study

The OPUS 20 study is a randomized phase II trial, comparing FOLFOX vs. FOLFOX + cetuximab in the first line of metastatic colorectal cancer treatment. The sample size was 292 patients, randomized 1: 1 by ECOG status.

Its design considered superiority in the percentage of response in the experimental arm as a primary objective. The efficacy analysis according to KRAS status was, as in CRYSTAL, retrospective.

In the past ECCO / ESMO (Berlin, 2009), updated efficacy data of the combination of FOLFOX-4-cetuximab in patients with native KRAS was presented, after increasing the number of patients in whom the determination of mutational status was performed. (93.5%) (Bokemeyer C, Bondarenko I, Hartmenn JT, et al. Overall survival of patients with KRAS wild-type tumors treated

with FOLFOX-4 ± cetuximab as 1st line treatment of metastatic colorectal cancer: the OPUS study. Updated information presented at the 15th Congress of the European cancer Organization / 34th Congress of the European Society of Medical Oncology. Abstr. 6079). In these patients, the median overall survival was 22.8 months in the cetuximab arm, compared to 18.5 months in the QT alone arm ($p = 0.38$). The updated global response data was 57.3% in the patients treated with cetuximab vs 34% in the other arm ($p = 0.027$) and progression-free survival was 8.3 months in the arm that associated cetuximab, maintaining 7.2 months achieved in patients treated only with CT (HR = 0.57, 95% CI (0.38-0.86), $p = 0.0064$), which represents a 43% reduction in the risk of disease progression.

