4.6 OBJECTIVES

4.6.1 Principal Objective

Validation of the biomarkers BRAF, IGF1P / MMp7 (DP) and PI3K-PTEN to predict PFS in patients with advanced and / or metastatic colorectal cancer with non-mutated KRAS treated with standard chemotherapy plus biweekly cetuximab as first-line therapy.

To identify new biomarkers that can predict progression-free survival (PFS) in non-mutated KRAS patients treated with biweekly chemotherapy (QT) and cetuximab in first-line therapy.

The need to identify additional biomarkers of cetuximab efficacy stems from the small predictive value of the current classification, based on KRAS mutational status, of the efficacy of biweekly cetuximab administration in the group of patients with the disease under study.

The proposed biomarkers are:

- 1 BRAF mutations
- 2.IGF-1Rp / MMP-7 (DP)
- 3.PIK3CA-PTEN.

Identifying additional factors that determine the efficacy of biweekly cetuximab will provide the scientific community with additional stratification factors for clinical trial design and better patient selection for biweekly cetuximab treatment.

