6.4 Treatment assignment

The selection of treatment between FOLFOX-6 (m) + biweekly cetuximab or FOLFIRI (m) + biweekly cetuximab will be made by the Principal Investigator, according to the usual clinical practice of his center.

Single-arm, multicenter, prospective phase II clinical trial for biomarker validation in patients with advanced and / or metastatic colorectal cancer with non-mutated KRAS gene treated with chemotherapy plus biweekly cetuximab as first-line therapy

After confirmation of eligibility, the center's staff will fax an inclusion request form to the Sponsor (GEMCAD Technical Secretariat [REDACTED]) in which they must record the treatment chosen by the Principal Investigator for the patient.

The GEMCAD Technical Secretariat will return a communication to the center to confirm that a new patient has been registered in the study.

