Tumour sample quality from primary or metastatic tissues was checked, and blood samples were collected at baseline and every 3 months along with abdominopelvic CT scan imaging. The feasibility of bi-weekly cetuximab in combination with chemotherapy (FOLFOX or FOLFIRI) was evaluated by means of progression free survival (PFS), overall survival (OS), objective response rate (ORR), and reported toxicities. The trial hypothesis was that the proposed biomarkers would allow identifying those patients who would benefit the most from bi-weekly cetuximab therapy. KRAS and NRAS mutations were evaluated by pyrosequencing, BRAF and PI3K mutations by RT-qPCR, and PTEN expression by immunohistochemistry. The PFS (time from the signature of the ICF date to PD or death) and OS (time from the signature of the ICF date to death) were analysed and compared between patients with: wild-type (wt) BRAF (wt-BRAF) vs mutant BRAF, and in patients with increased PI3K pathway activation (PI3K mutant or loss of PTEN expression) vs low PI3K pathway activation (wtPI3K and preserved PTEN expression).

Sponsor: Grupo Español Multidisciplinar en Cáncer Digestivo (GEMCAD) Spanish Multidisciplinary Group in Digestive Cancer

Protocol number: GEMCAD 1002 - POSIBA

Clinical Phase: II

Study dates: Study initiation date: first patient enrolled on 27/JUN/2011
Study completion date (last patient completed): 20/JUN/2017

[figure not shown]
This study, including the archiving of essential documents, was performed in compliance with ICH Good Clinical Practice (GCP)

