6.5.2. DETERMINATION OF SAMPLE SIZE

It was the aim of the study to identify two groups based on the well-established categories of clinical variables and the proposed biomarkers which are prognostic regarding PFS. The sample size should be sufficient detect a clinically relevant difference in PFS with a log-rank test between the two groups, given the following assumptions:

- The difference in PFS at 12 months between the two groups is at least 20% (i.e. 50% vs 30%) corresponding to a hazard ration of 1.79 assuming an exponential distribution. • Alpha error (two-tailed): 5%
- Beta error: 20%
- Monthly recruitment: 8 patients
- Percentage of patients with classification= 0: 40%

Initially, the number of patients required to be recruited in 24 months was 155 for 115 events to occur. Assuming a 10% proportion of potentially non-assessable patients, a total of 170 patients were needed to be included. After recruiting 157 patients, it was determined that about 70 of these patients had insufficient samples for biomarker analysis preventing their inclusion into the analysis of the primary objective. Therefore, in order to observe the 115 events necessary to evaluate the primary endpoint, the total number of patients was increased up to 221 recruited in 47 months (4–5 patients per month). Finally, the total study duration was 70 months (recruitment + follow-up).

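### The hypothesis and intended use promise to identify who benefits from cetuximab, but with every patient on cetuximab the design can show only prognosis under treatment

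*Protocol*

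**What the plan says.** **Design.** The Protocol synopsis describes a "Single-arm prospective phase II clinical trial". Under Protocol 6.4, "The selection of treatment between FOLFOX-6 (m) + biweekly cetuximab or FOLFIRI (m) + biweekly cetuximab will be made by the Principal Investigator", so both options contain cetuximab. SAP 6.5.1.3 lists patients who did not receive cetuximab among those who cannot contribute to the primary objective.

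**Hypothesis and intended use.** The synopsis and Protocol 4.5 hypothesise that the markers will "select those patients who will benefit the most from biweekly cetuximab treatment". Protocol 4.6.1 speaks of biomarkers of cetuximab efficacy and promises "better patient selection for biweekly cetuximab treatment". The synopsis (Statistical considerations) and Protocol 10.1 call the markers predictive. The SAP title page (Study description) says "the proposed biomarkers would allow identifying those patients who would benefit the most from bi-weekly cetuximab therapy". SAP 5.1 repeats the efficacy and selection statements, and SAP 4.2 (justification of the biomarkers) mentions treatment selection.

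**Objective and analysis.** The core primary objective is narrower: to predict PFS in patients who all receive chemotherapy and cetuximab. Protocol 10.2.1 compares PFS between two classified cohorts. SAP 6.5.1.1 compares AUCs for 12-month PFS with and without each marker. SAP 6.5.2 aims for groups "which are prognostic regarding PFS".

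Neither document contains a sentence limiting the inference to prognosis.

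**The concern.** A marker identifies who benefits from cetuximab only if the effect of cetuximab differs by marker status. That is a marker-by-treatment interaction, and it needs outcomes without cetuximab in each marker group. The trial collects none.

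The Protocol reports from a first-line randomised trial that "the presence of mutated BRAF worsened the results, regardless of the treatment used" (section 4.1), which describes a prognostic marker. If the classification separates PFS as planned, the hypothesis as worded invites the reader to treat the gap as differential benefit. The same gap could exist without cetuximab.

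**Working it through.** **1. What the sample size powers.** Inputs from Protocol 10.2.5: 12-month PFS 60% vs 40%, two-sided 5%, 80% power, 40% of patients in class 0, 115 events.

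- Hazard ratio under exponential PFS: ln(0.40)/ln(0.60) = 0.9163/0.5108 = 1.794.
- Freedman's formula for unequal groups, with k = 60/40 = 1.5 (poorer to better): events = (1.960 + 0.842)² × (1 + k·HR)² / [k(1 − HR)²] = 7.849 × 13.62 / 0.945 = 113.1, so 114.

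This is within 1% of the stated 115. It assumes that class 0 is the better group, which the Protocol does not say. The reverse gives 90.1 (91 events), and Schoenfeld's formula gives 96. On any version the contrast is one marker group against another with everyone treated. It contains no cetuximab effect.

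**2. What the hypothesis needs.** Let S₁ and S₀ be 12-month PFS with and without cetuximab. Benefit in a marker group is S₁ − S₀. The difference in benefit, better minus poorer group, is

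[S₁(better) − S₁(poorer)] − [S₀(better) − S₀(poorer)] = 20 points − G₀,

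where G₀ is the marker gap without cetuximab. The trial estimates the first bracket and has no data on the second.

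**3. How much G₀ matters.** The values without cetuximab below are assumptions chosen to show the range. None comes from the documents.

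| Without cetuximab, better/poorer, against 60/40 with it | Same pattern against the SAP's 50/30 | G₀ | Benefit, better group | Benefit, poorer group |
|---|---|---|---|---|
| 60/40 | 50/30 | 20 | 0 | 0 |
| 45/25 | 35/15 | 20 | 15 | 15 |
| 40/40 | 30/30 | 0 | 20 | 0 |
| 60/20 | 50/10 | 40 | 0 | 20 |

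All four rows give the same data in this trial. In the last row the group with the shorter PFS is the only one that benefits. More patients narrow the interval around the 20 points and leave G₀ unknown.

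**4. Is a non-zero G₀ plausible on the documents' own evidence?**

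- BRAF: the finding quoted above, after which the cited authors called the mutation a negative prognostic factor (Protocol 4.1; SAP 4.1.2).
- Clinical variables: Protocol 4.5 says that good performance status with normal LDH goes with better PFS and OS whatever the therapy. Both enter the classification (Protocol 10.4).
- Double-positive phenotype: Protocol 4.4.2 reports fourfold higher MMP-7 in oxaliplatin-resistant cells, so a gap could partly reflect chemotherapy resistance. The clinical data cited there come only from patients given an anti-EGFR antibody.

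By contrast, SAP 4.1.1 supports extended RAS testing with a trial that compared FOLFOX with and without an anti-EGFR antibody.

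**5. Scale of a trial that could answer the question (illustration only).** With 1:1 randomisation to cetuximab or not, a 40:60 marker split, two-sided 5% and 80% power, an interaction test needs 4 × 7.849 / [0.4 × 0.6 × (ln R)²] events, where R is the ratio of hazard ratios. An assumed R of 1.79 gives 386 events; R = 1.5 gives 796 and R = 2.5 gives 156.

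**The case against.** The strongest reply is that the plan is already prognostic where it counts. The core primary objective concerns PFS in treated patients. The SAP primary analysis asks whether markers add to clinical variables in predicting 12-month PFS. SAP 6.5.1.5 uses Cox regression to find prognostic factors and compares the scores for prognosis. Protocol 4.4.3 says that the interest in BRAF lies in its weight among other prognostic markers. The single-arm design is disclosed throughout. All of this stands, and it confines the problem to the hypothesis and the statements of intended use.

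Four stronger readings are tempting, and the documents do not support them.

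- *The trial draws an unsupported conclusion.* The texts are a hypothesis and an intended use. The Conclusions heading in the SAP synopsis is empty.
- *The trial has zero power for its hypothesis.* Power belongs to a specified test, and no interaction test is planned. The accurate term is not identifiable.
- *The plan would lead to cetuximab being withheld.* No passage proposes this. The same sentence of Protocol 4.6.1 also names stratification in later trials, which prognostic markers can serve.
- *The markers are known to be purely prognostic.* The evidence quoted concerns BRAF only and does not settle the other two pathways.

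An appeal to phase II status does not help, because the limit is one of identification and not of precision.

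**Conclusion.** The point holds for the hypothesis and intended use. The statements that the markers identify who benefits most from biweekly cetuximab, determine its efficacy or guide selection for it claim something a single-arm trial cannot show at any sample size. With a 20-point PFS gap under treatment, the difference in benefit is 20 − G₀ points. It runs from +20 through 0 to −20 over the illustrative range of G₀ from 0 to 40, and the trial supplies no information on G₀.

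This rests on two facts in the documents: all patients in the efficacy analysis receive cetuximab, and no control comparison is planned. It does not depend on the sample size calculation, which broadly reproduces. A reader might infer that the primary objective or the SAP analyses are invalid. They are not: read as prognosis under treatment, both are supportable.

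**What to change.** 1. Restate the hypothesis and intended use as *prognostic for PFS among patients receiving chemotherapy and biweekly cetuximab*. The places are Protocol synopsis (Clinical Hypothesis), 4.5 and 4.6.1, and SAP title page (Study description), 4.2 and 5.1. Remove the statements there on benefit from, efficacy of, or selection for cetuximab.
2. Replace 'predictive' in the synopsis (Statistical considerations) and Protocol 10.1. Search both documents for other uses in the sense of treatment benefit.
3. Add one sentence to the primary objective saying that 'predict' means prognosis under the study treatment.
4. Add one sentence to the analysis plan and report saying that these results alone cannot show differential benefit from cetuximab.
5. Keep the statement about stratification factors for later trials.

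No endpoint, analysis, sample size or procedure changes. The cost is editing and a narrower claim.
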